8.4 Analysis Plan

8.4.1 Baseline and Demographic Analysis

The disposition of all subjects (number of subjects enrolled, treated, completed, discontinued and replaced) will be presented. Demographic and baseline subject characteristics will be summarized (e.g., age, race, ethnicity, ECOG Performance Score, prior medical history, prior therapy and response to prior therapy).

8.4.2 Safety Analysis

The Safety Analysis Set will consist of all subjects who received at least 1 dose of Sacituzumab Govitecan.

Safety parameters will include results of AE reporting, physical exam findings, vital signs, safety laboratory determinations and ECGs. AEs will be listed according to the MedDRA coding dictionary by system organ class, preferred term and high level terms. All AEs will be classified by type, severity, and causality. In addition to all AEs, SAEs, drug-related AEs, Grade 3 or higher AEs, drug-related Grade 3 or higher AEs, and AEs leading to discontinuation or death will be described. A customized drug dictionary will be used to classify concomitant medications by therapeutic class and preferred term.

Changes from baseline assessments (e.g., laboratory parameters, vital signs and ECG parameters) will be presented using descriptive statistics. The distribution of the maximum observed grade of each AE will be tabulated. Toxicities will be summarized by type and severity in tabular format. Toxicity rates (Grade 2, Grade 3, Grade 4, Grade \geq 2, Grade \geq 3, etc.) will be calculated and reported along the corresponding 95% confidence intervals. The 95% confidence intervals will be constructed using the Wilson score method.

The safety analyses will be stratified by subjects who continued single agent ARSI in combination with Sacituzumab Govitecan and patients who discontinued single agent ARSI before starting Sacituzumab Govitecan.

8.4.3 Efficacy Analysis

The Efficacy Analysis Set will consist of all subjects who receive at least 1 dose of Sacituzumab Govitecan and have at least 1 post-dose assessment of PSA; and/or 1 post-dose radiographic assessment for subjects with evaluable and/or measurable metastases at screening, 1 post-dose assessment of metastatic disease will be required. Subjects who

discontinue study participation early so they do not meet criteria for inclusion in the efficacy analysis set can be replaced.

Changes in PSA will be compared to baseline and maximal change from baseline and change at Week 9 (e.g., end of Cycle 3) will also be determined, as will duration of response. Maximum change in soft tissue lesions as seen on CT or MRI of the chest, abdomen and pelvis, as well as changes on bone scintigraphy according to the PCWG2 criteria will also be compared to baseline, and summarized.

A subgroup efficacy analysis will be conducted in the group of patients who continued single agent ARSI in combination with Sacituzumab Govitecan.

Definition and analysis of primary efficacy endpoint:

PSA response rate: Subjects who achieve $\geq 50\%$ PSA decline at or before 9 weeks of therapy with Sacituzumab Govitecan are considered to have responded. PSA responses will be analyzed by descriptive statistics and summarized in tabular format (frequency tables). The overall PSA response rate will be reported along with the corresponding 95% confidence interval which will be constructed using the Wilson score method.

6-month rPFS rate: Proportion of subjects remaining alive and progression free (using PCWG2 criteria) 6 months from time of starting treatment as estimated by the Kaplan-Meier method. The point estimate of the 6-month rPFS rate will be reported along with the corresponding two-sided 95% confidence interval.

Definition and analysis of secondary efficacy endpoints:

- i. *Median rPFS.* The probability distribution of PFS will be estimated using the Kaplan-Meier method. The median will be estimated from this distribution. Subjects who have not died or progressed (using PCWG2 criteria) will be censored at the date of last assessment.
- ii. *Median OS.* OS is the duration from start of treatment until death from any cause. The probability distribution of OS will be estimated using the Kaplan-Meier method. The median will be estimated from this distribution. Subjects who have not died will be censored at the date of last contact.

Response. The number and frequencies of subjects with progressive disease, stable disease, partial response and complete response will be summarized in tabular format. The overall response rate will be reported along with the corresponding 95% confidence interval which will be constructed using the Wilson score method.

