ECOG performance status assessments (Appendix A) are required to assess subject functional status for study eligibility purposes and will be performed throughout the study according to the schedule of procedures.

5.2.7 *ECG*

A 12-lead ECG will be obtained at screening and at the end of study visit. It is not necessary to do ECGs 5 minutes apart. Additional unscheduled 12-lead ECG may be conducted when necessary at the investigator's discretion.

5.3 *Determination of Extent of Metastatic Disease*

All subjects will undergo an extent of disease evaluation consisting of bone scintigraphy, CT of the chest, CT of the abdomen and pelvis, and other regions of known/suspected involvement, at Screening unless already conducted within 30 days of Cycle 1, Day 1. CT scans should be performed with contrast unless contraindicated. MRI abdomen and pelvis with contrast may be done in situations where a CT with contrast is equivocal or contraindicated. A non-contrast chest CT should be done for subjects requiring an MRI of the abdomen and pelvis.

Subjects will undergo repeat evaluations of their extent of disease every 9 weeks (\pm 7 days) if they remain progression- free on study. Imaging modality should remain consistent by lesion throughout the study.

5.4 *Laboratory Evaluations*

On treatment days, blood samples should be collected prior to infusion. Laboratory tests will be performed by local labs and will include:

5.4.1 *CBC*

A CBC will consist of determinations of hemoglobin (HGB), hematocrit (HCT), white blood cells (WBC), red blood cells (RBC), neutrophils, lymphocytes, monocytes, eosinophils, basophils, and platelet count. Absolute values are preferred.

5.4.2 *Coagulation factors*

Partial thromboplastin time (PTT) and prothrombin time (PT) or international normalized ratio (INR) will be obtained according to the schedule of procedures and at any other visit where clinically indicated.

5.4.3 *Comprehensive metabolic panel (CMP)*

A CMP will consist of determinations of sodium, potassium, chloride, bicarbonate, blood urea nitrogen (BUN), glucose, creatinine, aspartate transaminase (AST), alanine transaminase (ALT), alkaline phosphatase, lactate dehydrogenase, total bilirubin, total protein, albumin, serum calcium, magnesium, and phosphorous.

5.4.4 *Urinalysis*

Urinalysis will include pH, specific gravity, and hemoglobin, glucose, ketones, and protein by dipstick, with microscopic exam if any of the dipstick analytes are 2+ or higher.

5.4.5 *PSA*

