8.3 Determination of Sample Size

The primary endpoints for the study are (1) PSA response rate, which is defined as the proportion of subjects achieving a $\geq 50\%$ decline in PSA at or within 9 weeks of starting Sacituzumab Govitecan. Prior published data from retrospective studies report PSA response rates ($\geq 50\%$ decline) in 20-30% of subjects on 2nd line AR directed therapy after progression on a 1st line agent in the pre-docetaxel setting (3-8), (2) and the 6-month rPFS rate. The response rate appears higher with cytotoxic chemotherapy. Although data are limited in the pre-docetaxel setting, retrospective studies in the post-docetaxel setting suggest patients with prior response to abiraterone are more likely to respond to second line enzalutamide (9-11). The familywise type I error for the two primary endpoints of the study is one-sided 0.05 and a Bonferroni adjustment for evaluating two primary endpoints will be applied that each endpoint will be tested at the one-sided 0.025 (0.05/2) significance level. A PSA response rate of 20% or less will be considered as unacceptably low. A PSA response rate of 40% or more, on the other hand, will be considered sufficient evidence to consider further clinical trial investigation. Hence, the null hypothesis that the PSA response rate is 20% will be tested against the alternative hypothesis that the PSA response rate is 40%. A sample size of 45 evaluable subjects for PSA response (defined as subjects who received at least 1 dose of Sacituzumab Govitecan and have at least 1 post-dose assessment of PSA) is required to detect an increase in the PSA response rate from 20% to 40% with 87% power at the one-sided exact test with a significance level of 0.025. Analogously, a 6-month rPFS rate of 20% or less will be considered as unacceptably low and 40% or more considered sufficient evidence. Again a sample size of 45 evaluable subjects (for assessing 6-month PFS rate) is required to detect an increase in the 6-month rPFS rate from 20% to 40% with 87% power at the one-sided 0.025 significance level. The following table shows the probabilities for rejecting the null hypothesis with a sample size of 45 evaluable subjects, assuming that the true PSA response/6-month rPFS rates range between 35-50%.

Table 10. Attainable power levels with a sample size of 45 evaluable subjects

True PSA response/6-months PFS rate	Probability of rejecting null hypothesis
35%	68%
40%	87%
45%	96%
50%	>99%

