Hence, a sample size of 45 evaluable subjects will provide between 68-99% power to detect a true PSA response rate or 6-month rPFS rate between 35-50% at the one-sided 0.025 significance level.

A sample size of 45 subjects will also be adequate for estimating toxicity rates with sufficient accuracy. Specifically, toxicity rates will be estimated with a standard error of less than 8% and the corresponding 95% confidence intervals will be no wider than 30%.

In order to account for unevaluable (for assessing PSA response or 6-month rPFS rate) subjects, 55 subjects in total will be enrolled.

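### On two of three readings of 8.4.3, a treated subject who dies before the first post-dose scan drops out of 6-month rPFS, although death is an rPFS failure

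*Combined protocol and SAP*

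**What the plan says.** Section 8.4.3 opens with one Efficacy Analysis Set. It requires at least one dose and one post-dose PSA, then continues after an and/or with "1 post-dose radiographic assessment for subjects with evaluable and/or measurable metastases at screening, 1 post-dose assessment of metastatic disease will be required". On replacement, the section provides that those who "discontinue study participation early so they do not meet criteria for inclusion in the efficacy analysis set can be replaced".

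The same section defines the 6-month rPFS rate as "Proportion of subjects remaining alive and progression free (using PCWG2 criteria) 6 months from time of starting treatment as estimated by the Kaplan-Meier method". For median rPFS it adds "Subjects who have not died or progressed (using PCWG2 criteria) will be censored at the date of last assessment". Death is therefore an event, not a reason for censoring.

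Section 8.3 states that "a sample size of 45 evaluable subjects (for assessing 6-month PFS rate) is required" but never says what makes a subject evaluable for rPFS. For PSA response it does: "defined as subjects who received at least 1 dose of Sacituzumab Govitecan and have at least 1 post-dose assessment of PSA". It then adds "In order to account for unevaluable (for assessing PSA response or 6-month rPFS rate) subjects, 55 subjects in total will be enrolled".

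Inclusion criterion 3.1.2 requires documented metastatic disease. On imaging, section 5.3 says "Subjects will undergo repeat evaluations of their extent of disease every 9 weeks", and Appendix B places the first on-study scans at Cycle 3 Day 15.

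**The concern.** The set definition allows three readings.

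- **(a) Strict.** Every subject with metastases, so in effect every subject, needs a post-dose scan to be in the set.
- **(b) Endpoint-specific.** PSA response needs a PSA and rPFS needs a scan. Section 8.3 supports this, because it speaks of subjects evaluable or unevaluable for each endpoint.
- **(c) Either suffices.** A post-dose PSA or a post-dose scan is enough.

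On (a) and (b), a treated subject who dies before about week 9 is outside the rPFS analysis. On (c), only subjects with neither assessment are lost, for example those who die before the first scheduled post-dose PSA at Cycle 1 Day 8.

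A subject who stops early but lives can still be scanned at the End of Treatment visit (5.8, Appendix B). A subject who has died cannot. The scan requirement therefore removes mainly failures, and the bias in a primary endpoint runs upward. As written, an analyst could treat such a death either as a failure or as a missing subject.

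A secondary point: reading (a) would also require a scan for the PSA denominator, which 8.3 does not. Reading (b) removes that conflict.

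**Working it through.** **Inputs.** From 8.3: null rate 20%, alternative 40%, one-sided alpha 0.025 per endpoint, 45 evaluable subjects, 55 enrolled. The number of deaths before the first scan, k, is not in the documents and is assumed to be 1, 2, 3 or 5.

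**Plan's own figure.** The smallest r with P(X ≥ r | 45, 0.20) ≤ 0.025 is 15, with exact size 0.02499. Exact power is P(X ≥ 15 | 45, 0.40) = 0.857. A normal approximation with the null variance gives 67.9%, 87.3%, 96.4% and 99.3% at true rates of 35%, 40%, 45% and 50%. That matches Table 10, so the stated 87% is reproduced.

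**Deaths dropped and replaced to 45.** If the true rate among all 45 + k treated subjects is 20%, the rate among the 45 retained is 0.20 × (45 + k)/45. Type I error is P(X ≥ 15 | 45, that rate). The Kaplan-Meier columns come from simulation (200,000 trials): progression at week 9 or 18, early deaths uniform over weeks 1 to 8.5, and success if the lower bound of the two-sided 95% interval at 26 weeks exceeds 0.20. Section 8.4.3 names no interval method, so log-log Greenwood is an assumption.

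| k | Expected rate | Binomial | KM, about 10% censored | KM, about 20% censored |
|---|---|---|---|---|
| 0 | 20.0% | 0.025 | 0.019 | 0.019 |
| 1 | 20.4% | 0.030 | 0.023 | 0.022 |
| 2 | 20.9% | 0.036 | 0.027 | 0.027 |
| 3 | 21.3% | 0.042 | 0.032 | 0.032 |
| 5 | 22.2% | 0.058 | 0.045 | 0.043 |

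With the deaths kept as events, the simulated error is 0.013 to 0.021 in all these cases, including no censoring. At about 10% censoring, the error for k = 0 to 5 rises from 0.015 to 0.036 with plain Greenwood intervals and from 0.041 to 0.086 with log intervals. The direction is the same for all three methods.

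**Deaths dropped, no replacement.** With N treated, the retained rate is 0.20 × N/(N − k), and the exact threshold is reset for N − k.

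| N treated | k = 1 | k = 2 | k = 3 | k = 5 |
|---|---|---|---|---|
| 45 | 0.025 | 0.024 | 0.024 | 0.049 |
| 50 | 0.014 | 0.030 | 0.030 | 0.058 |
| 55 | 0.018 | 0.018 | 0.036 | 0.035 |

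**A borderline result.** A just-positive 15/45 (p = 0.025) becomes 15/46 (p = 0.030), 15/48 (p = 0.044) or 15/50 (p = 0.061) when 1, 3 or 5 deaths are restored as failures.

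**PSA response under reading (a).** P(X ≥ 14 | n, 0.20) is 0.052 at n = 45, 0.030 at n = 42 and 0.024 at n = 41. Four subjects would have to drop out before the conclusion changed.

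**The case against.** The best counter-argument is that 8.4.3 never says rPFS is estimated only in the Efficacy Analysis Set. Taken alone, the endpoint definition and the censoring rule make a death at week 5 an event. Reading (c) follows the printed and/or, and three possible readings say nothing about which is likely. Section 6.3.1 also speaks of subjects who have evaluable and/or measurable metastases as though they were a subset. These points show that exclusion is not certain. They do not remove the problem: this is the only efficacy set, it opens the efficacy section, 8.3 expects some subjects to be unevaluable for rPFS, and no text keeps an early death in the analysis.

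The size objections largely stand. Replacement of deaths is an inference, because the rule covers early discontinuation and neither names nor exempts death. Without replacement there is no inflation at 1 to 3 deaths with 45 treated, or at 1 or 2 with 55 treated. The unspecified interval method moves the error at zero deaths from 0.015 to 0.041, more than dropping one to three deaths does under log-log. Entry requires ECOG 0-1. The nearest figure in the documents is Grade 5 adverse events in 20 of 420 subjects (4.8%, Table 3), which scales to 45 × 20/420 ≈ 2. It comes from other tumours, has no nine-week limit and may not count deaths from progression, but it lends no support to the five-death case. Replaced subjects would also be visible in the disposition table (8.4.1).

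**Conclusion.** The concern holds and should be fixed. On readings (a) and (b), a treated subject who dies before the first scan is left out of an endpoint that counts death as failure; on (c), only the earliest deaths are lost. The bias in the estimate is upward. It amounts to 0.4 to 1.3 percentage points for 1 to 3 deaths and 2.2 for five, under a true all-treated rate of 20% and replacement to 45. The type I error then reaches 0.030 to 0.058 by the binomial rule and 0.022 to 0.045 by Kaplan-Meier with 10% to 20% censoring (log-log intervals). At one death the Kaplan-Meier error stays below 0.025. These figures rest on assumed death counts, so the effect may be small. The case for the change is that a primary analysis should not leave open how a death is counted. Confidence is medium, because the text can be read in more than one way.

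**What to change.** In 8.4.3, replace the set definition with one sentence per endpoint.

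- **6-month and median rPFS:** all subjects with at least one dose, by Kaplan-Meier from first dose. Death before any scan is an event at the date of death. Living subjects who leave without documented progression are censored.
- **PSA response:** the 8.3 denominator (one dose and one post-dose PSA), with no scan required. As an optional sensitivity analysis, report all treated subjects with a missing post-dose PSA counted as non-response.
- **Replacement:** it may stay, but enrolling a replacement does not remove a subject who died from the rPFS analysis.

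Align the evaluability wording in 8.3.

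**Cost.** Wording only, within the planned 55 subjects. The rPFS estimate may be slightly lower. Any count-based threshold must follow the number analysed: 16 for 46 to 48, 17 for 50, 18 for 55. If 40% is the all-treated rate, exact power is 0.81, 0.84, 0.86 and 0.84 at 46, 47, 48 and 50 analysed, and 0.89 at 55 (exact size 0.018), against 0.86 at 45 now. If 40% holds only among subjects who survive to a scan, 45 such subjects plus 1, 2, 3 or 5 deaths give power of 0.78, 0.78, 0.78 or 0.67. With 55 treated in total it is 0.87, 0.85, 0.82 or 0.76. Analysing all 55 therefore protects power best.

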2. OBJECTIVES

2.1 Primary Objective

- To determine the proportion of subjects who have ≥50% PSA decline at or within 9 weeks of starting treatment with Sacituzumab Govitecan.
- To determine the 6-month rPFS rate

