5.8 Criteria for Removal from Protocol Treatment

Every effort should be made to keep subjects on study drug for a minimum of 9 weeks (i.e., 3 cycles) unless withdrawal of informed consent, the presence of significant toxicity, clear progression of neoplastic disease, or any other reason for the removal from study as outlined in this section. Per the PCWG2 guidelines, "in the absence of clinically-compelling indicators of disease progression, early changes (within 9 weeks) in indicators such as serum PSA, patient-reported pain, and radionuclide bone scan should be ignored". With respect to bone scan changes, 72% of the apparent disease progressions, in the abiraterone acetate plus prednisone vs. placebo plus prednisone registration trial, proved to be responders and were able to continue therapy. In contrast, unequivocal signs of disease progression such as spinal cord compression or pain requiring a change in therapy would require discontinuation of Sacituzumab Govitecan prior to 9 weeks (i.e., before completing Cycle 3).

Subjects who require palliative radiotherapy for focal symptom relief may remain on study as long as the treating investigator feels they are deriving benefit from Sacituzumab Govitecan 2 and the radiotherapy is not to a target or non-target lesion recorded at baseline.

Subjects may be removed from protocol treatment under the following conditions:

- First documentation of progressive disease or symptomatic deterioration indicating treatment failure.
 - Discontinuation is subject to the goal of not removing subjects prior to completing 9 weeks of treatment especially for the lone reason of rising PSA. Subjects with rising PSA may continue on study beyond Cycle 3 at the discretion of the investigator.

- Subjects who want to continue treatment after radiological documentation of progressive disease should notify the physician who will obtain Sponsor approval before treatment continuation.
- Unacceptable toxicity, or any AE, which in the opinion of the investigator precludes further participation in the study.

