6.4 Dose modification of Sacituzumab Govitecan

The current established dose schedule for Sacituzumab Govitecan is 10 mg/kg on days 1 and 8 repeated every 21 days given as an intravenous infusion at the rates described in Section 6.3.3. There should be a minimum of 14 days between the day 8 infusion and the day 1 infusion of the next cycle in the absence of progression of disease or unacceptable toxicity. Planned deviations in treatment schedule are allowable up to 7 days due to holidays, vacations or personal reasons. The protocol allows aggressive medical management of patients in order to avoid dose reduction and dose delay as much as possible. Growth factors should be initiated once the ANC starts decreasing and may be used prophylactically as clinically indicated. In patients who would be considered high risk for neutropenia (those who experienced febrile neutropenia or Grade 3-4 neutropenia with prior treatments), use of growth factors should be initiated early on and used prophylactically as early as Cycle 1. Growth factors are required at cycle 1 for all patients \geq 65 years old.

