- c. ALT or AST >3x ULN and total bilirubin >2x ULN or INR >1.5

Patients with life threatening, grade 3 non-hematologic toxicity regardless of relationship to study drug should discontinue study treatment permanently. Examples include myocardial infarction or stroke.

In the event of other Grade 3 treatment-related toxicity at the time of a scheduled treatment day, the dose will be held and subjects will be assessed at least weekly. If recovery to \leq Grade 1 delays the next dose by only one week, treatment may resume then without dose reduction. If recovery to \leq Grade 1 delays the next dose by 2 or 3 weeks, treatment must be resumed at a reduced dose (Table 7). If treatment on day 8 of a cycle is held, the dose should be skipped and treatment resumed with day 1 of the following cycle. If treatment on day 1 is delayed, the entire cycle should be delayed, maintaining the same cycle number. The use of prophylactic G-CSF in subsequent cycles is recommended to prevent recurrence of neutropenia that would require a dose reduction. If recovery to \leq Grade 1 requires more than a three-week delay, treatment must be permanently discontinued.

After **cycle 1 day 1** treatment initiation should be withheld until ANC is $> 1000 / \mu\text{L}$. If day 8 is held for ANC $< 1000 / \mu\text{L}$, that dose will be missed. Resume dosing with next cycle. If delay more than 4 weeks, discontinue treatment. GCSF prophylaxis prior to cycle 2 is recommended if clinically appropriate.

For grade ≥ 3 neutropenia (ANC $< 1000 / \mu\text{L}$) after cycle 1 day 1 or after day 1 of subsequent cycles, hold day 8, initiate growth factor support and administer prophylactic growth factors with each subsequent cycle. Resume dosing with the next cycle only if toxicity resolves. **In subsequent treatment cycles**, treatment initiation for Day 1 of the cycle should be withheld until ANC $> 1000 / \mu\text{L}$ and GROWTH FACTORS should be used as clinically indicated. Patient will be assessed weekly for grade 3 ANC (ANC $< 1000 / \mu\text{L}$ to $500 / \mu\text{L}$) and bi-weekly for grade 4 ANC (ANC $< 500 / \mu\text{L}$). If delay more than 3 weeks, discontinue. Resume dosing at the next cycle if toxicity recovers to \leq grade 2 within 3 weeks. All subsequent cycles should be administered with growth factor support.

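### The PSA co-primary closes at 9 weeks, but a subject whose cycle has slipped may have no scheduled PSA at that point; the loss is probably small and the fix is cheap

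*Combined protocol and SAP*

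**What the plan says.** **Endpoint.** Section 2.1 sets the co-primary as a 50% "PSA decline at or within 9 weeks of starting treatment with Sacituzumab Govitecan". Section 8.3 uses the same clock for the tested rate: "decline in PSA at or within 9 weeks of starting Sacituzumab Govitecan". Section 8.4.3 words it as 9 weeks of therapy: "PSA decline at or before 9 weeks of therapy with Sacituzumab Govitecan are considered to have responded". No analysis window for the week-9 PSA is stated.

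**PSA schedule.** The Appendix B PSA row has screening, cycle 1 days 1 and 8, day 1 of every later cycle, end of treatment and follow-up. Day 1 visits have a window of 3 days either side. There is no PSA on day 8 or day 15 of cycle 3.

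**Delays.** Section 6.4.1: "If treatment on day 1 is delayed, the entire cycle should be delayed, maintaining the same cycle number". Section 5.8 allows delays of up to 3 weeks, and section 6.4 allows planned deviations of up to 7 days. Section 6.4 also says "There should be a minimum of 14 days between the day 8 infusion and the day 1 infusion of the next cycle".

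**Protection against delay.** Appendix B footnote 2 keeps the scans and the cycle 4+ CTC/plasma draw on a 9-week calendar when a cycle slips. Footnote 5 does likewise for the biopsy. Neither is attached to the PSA row.

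**Other uses of week 9.** Section 8.4.3 plans a descriptive PSA "change at Week 9 (e.g., end of Cycle 3". Section 5.8 asks sites to "keep subjects on study drug for a minimum of 9 weeks (i.e., 3 cycles". Appendix E asks for the percent PSA change at 9 weeks and, separately, the maximal change at any time.

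**The concern.** The endpoint runs on the calendar and its closing measurement runs on the treatment cycle. The two agree only while no day 1 visit has slipped. After a slip, cycle 4 day 1 can fall a week or more past the cut-off, and the last PSA that counts may be one to three weeks old at week 9.

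Such a subject has a post-dose PSA and so stays in the evaluable denominator of section 8.3. If he first reaches a 50% decline between his last in-window PSA and week 9, he is counted as a non-responder. That lowers the observed rate and the power of a co-primary test. The 9-week PSA change in Appendix E will also be missing for some delayed subjects. A PSA that was not drawn cannot be recovered at analysis.

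**Working it through.** **1. The plan's own figure.** Inputs from section 8.3: 45 evaluable subjects, null 20%, alternative 40%, one-sided exact test at 0.025.

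- P(X ≥ 14 | 45, 0.20) = 0.0521 and P(X ≥ 15 | 45, 0.20) = 0.02499, so the rule is to reject at 15 or more.
- Exact power is P(X ≥ 15 | 45, 0.40) = 85.7%. The plan states 87%; a normal approximation (score test) gives 87.3%. That difference is separate from this point, and 85.7% is the reference below.

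**2. Timing**, in elapsed days from cycle 1 day 1 with 21-day cycles.

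- Nominal: cycle 2 day 1 = 21, cycle 3 day 1 = 42, cycle 3 day 15 = 56, cycle 4 day 1 = 63 (window 60 to 66).
- Cycle 3 day 8 is day 49. Adding the 14-day minimum gives day 63, so cycle 4 day 1 has little room to come earlier unless a day 8 dose was early or skipped.
- The end-of-treatment PSA is 30 to 37 days after the last dose. For a last dose on cycle 3 day 1 or day 8 (day 42 or 49) it falls on days 72 to 86, so it does not fill the gap.

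| Delay | Last PSA by day 63 | Gap to day 63 | Cycle 4 day 1 |
|---|---|---|---|
| 1 week at cycle 2 or 3 day 1 | day 49 | 14 days | day 70 |
| 2 weeks at cycle 2 or 3 day 1 | day 56 | 7 days | day 77 |
| 3 weeks at cycle 2 or 3 day 1 | day 63 | 0 days | day 84 |
| Hold found at the cycle 4 day 1 visit, blood drawn | day 63 | 0 days | later |
| Cycle 4 day 1 delay known beforehand | day 42 | 21 days | later |

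An equal mix of the first three rows has a mean gap of (14 + 7 + 0)/3 = 7 days.

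**3. Effect on power.** Two inputs are assumptions, because the documents give neither:

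- f = share of subjects whose cycle 4 day 1 has slipped.
- G = share of responders who first reach 50% in the last 21 days, spread evenly over those days.

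Observed rate: p = 0.40 × (1 − f × G × gap/21). Power = P(X ≥ 15 | 45, p). Responders lost = 18 × f × G × gap/21, where 18 = 45 × 0.40.

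| f, G | Gap | p | Power | Responders lost of 18 |
|---|---|---|---|---|
| none | 0 | 0.4000 | 85.7% | 0 |
| 10%, 10% | 7 | 0.3987 | 85.3% | 0.06 |
| 10%, 10% | 14 | 0.3973 | 84.9% | 0.12 |
| 10%, 10% | 21 | 0.3960 | 84.4% | 0.18 |
| 20%, 20% | 7 | 0.3947 | 84.0% | 0.24 |
| 20%, 20% | 14 | 0.3893 | 82.2% | 0.48 |
| 20%, 20% | 21 | 0.3840 | 80.2% | 0.72 |

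The 7-day rows match the equal mix. The 21-day rows give every slipped subject the largest gap, which arises only when a cycle 4 day 1 delay is known beforehand.

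**The case against.** **The effect is limited.** This stands. Declines seen at cycle 1 day 8, cycle 2 day 1 or cycle 3 day 1 already count. A hold found at the cycle 4 visit will often still yield a PSA, since "On treatment days, blood samples should be collected prior to infusion" (section 5.4). A skipped day 8 dose does not move the cycle. The planned maximal PSA change will show a decline first seen at a late cycle 4 day 1. By-cycle PSA monitoring also follows Appendix E. None of this puts a week-9 PSA in the record of a subject who slipped.

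**Stronger readings that the documents do not support.**

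- *The primary endpoint has two definitions, so delayed subjects could get a longer response window and the type I error could rise.* The cycle wording in section 5.8 concerns time on drug, and in section 8.4.3 it illustrates the descriptive Week 9 change. No passage defines primary response by cycle count. Nine weeks of therapy in 8.4.3 is most naturally the clock of 2.1 and 8.3.
- *The time frame of the 20% null is unclear.* Section 8.3 defines the PSA response rate as a 9-week rate and then tests that rate. Whether the any-time benchmark in Table 1 suits it is another question.
- *A cycle 4 visit on days 64 to 66 is too late.* No passage imposes a strict day-63 cut, and the visit has its own 3-day window. A stated cut-off would settle the matter.
- *Table 2 shows that nearly half of subjects will be delayed.* Its 46.5% at 10 mg/kg counts adverse-event interruptions without limiting them to the first three cycles, may include day 8 holds, and omits other causes of delay. It is not a day 1 delay rate.

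**Conclusion.** The schedule does not secure the closing PSA of a co-primary endpoint for subjects whose day 1 visits slip, although the same calendar protects the scans, the later CTC/plasma draws and the biopsy against that slip. This follows from the text and needs no assumption.

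The size does rest on assumptions. At a mean gap of 7 days, the assumed shares cost 0.4 to 1.7 points of exact power. The least favourable row shown costs 5.5 points (85.7% to 80.2%). Larger shares would cost more, but the documents give no basis for choosing them. Under the 9-week calendar definition the bias is downward, so it can hide activity but cannot create a false positive. This is a cheap improvement, not a threat to the design.

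**What to change.** - **Appendix B.** Keep the day 1 PSA in every cycle. Add a separate note to the PSA row: one PSA at calendar week 9 (day 63, 3 days either side, from cycle 1 day 1) if cycle 4 day 1 does not fall in that window, drawn at an existing visit where possible. Do not simply attach footnote 2, which would thin the cycle 4+ PSA to every third cycle. Do not rely on the scan visit alone: its column is nominal day 56, footnote 6 allows 10 days either side and section 5.3 allows 7, so it can miss days 60 to 66.
- **Section 8.4.3.** Use the clock of sections 2.1 and 8.3, 9 weeks from starting drug, with PSA counted through day 66. For the descriptive Week 9 change, replace the end-of-cycle-3 gloss with the same calendar window.
- **Reporting.** State how many subjects have no PSA on days 60 to 66. A sensitivity analysis counting cycle 4 day 1 whenever drawn is optional, because the maximal PSA change largely covers it.

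Fix the rule before the PSA data are analysed. The cost is one calendar note, one definition and at most one extra local PSA per delayed subject. No sample size or decision rule changes. For subjects already past week 9, only the analysis rule and the reporting apply.
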